6.5.3.2. Management of Hypoglycemia Risk

Participants will be trained in the signs and symptoms of hypoglycemia and its treatment and instructed to record pertinent information about hypoglycemic events in their study diary.

Participants who develop persistent or recurrent unexplained hypoglycemia during the treatment period will be asked to reduce the dose or discontinue any concomitant AHM, starting preferably with the ones commonly associated with hypoglycemia (for example, sulfonylurea). Monitoring for hypoglycemia includes capture of events as described in Sections 8.3.2.1 and 10.4 Appendix 4.

6.6. Dose Modification

6.6.1. Tirzepatide

Tirzepatide is given QW by SC injection. There are no restrictions on the time of day each weekly dose of tirzepatide is given, but it is advisable to administer the SC injections on the same day of the week and similar time each week. If a dose of tirzepatide is missed, the participant should take it as soon as possible unless it is within 72 hours of the next dose, in which case, that dose should be skipped and the next dose should be taken at the appropriate time.

Study drug dose modification is not permitted, except for management of intolerable GI symptoms (see Section 6.6.2).

6.6.2. Management of Participants with Gastrointestinal Symptoms

Participants who experience intolerable GI symptoms (for example, nausea, vomiting, or diarrhea) at any time during the study should first be counseled on dietary behaviors that may help mitigate nausea and vomiting (for example, eating smaller meals, splitting 3 daily meals into 4 or more smaller ones, and stopping eating when they feel full) (see Section 10.9). If symptoms persist, the participant should be prescribed, at the investigator's discretion, symptomatic medication (for example, antiemetic or antidiarrheal medication). A temporary interruption of study drug for 1 dose is permitted, provided the participant has taken the last 3 weekly doses. Study treatment should be resumed immediately, either alone or in combination with symptomatic medication, which can also be utilized to manage symptoms. Management of study drug after interruptions >1 dose is discussed in Section 7.1.1.

If intolerable GI symptoms (for example, nausea, vomiting, or diarrhea) persist despite the above measures, the investigator should contact Lilly to consider reinitiating study drug at the next-lower maintenance dose in a blinded fashion (for example, 15 mg and 12.5 mg reduced to 10 mg, 10 mg or lower reduced to placebo). Only 1 dose reduction per participant will be permitted during the course of the study.

If intolerable GI symptoms persist despite symptomatic treatment, temporary drug interruption, and resumption at a lower dose of study drug, the participant should be discontinued from the study drug. All participants who discontinue study drug should continue to attend scheduled study visits. All dose adjustments will be managed through IWRS.

6.7. Intervention after the End of the Study

Tirzepatide will not be made available to participants after conclusion of the study.

7. Discontinuation of Study Intervention and Participant Discontinuation/Withdrawal

7.1. Discontinuation of Study Intervention

In rare instances, it may be necessary for a participant to permanently discontinue (definitive discontinuation) study intervention. If study intervention is definitively discontinued, the participant will remain in the study to be evaluated for any trial endpoint at the end of the study. See the SoA for data to be collected at the time of discontinuation of study intervention and follow-up and for any further evaluations that need to be completed.

Possible reasons leading to permanent discontinuation of IP:

- **Participant Decision**
 - The participant requests to discontinue IP
- **Clinical Considerations**
 - Initiation of open-label GLP-1R agonist, amylin analogues/agonists, or DPP-4 inhibitor, if participants will not or cannot discontinue them
 - Intolerable GI symptoms despite management as described in Section 6.6.2
 - BMI ≤ 18.5 kg/m² is reached at any time during the treatment period
 - Note:* The investigator should contact the sponsor CRP to discuss whether it is medically appropriate for the participant to continue study treatment.
 - Diagnosis of T1DM
 - Diagnosis of MTC or MEN syndrome type 2
 - Significant elevation of serum calcitonin (Section 8.3.2.4)
 - Diagnosis of acute or chronic pancreatitis
 - Diagnosis of an active or untreated malignancy (other than basal or squamous cell skin cancer, in situ carcinomas of the cervix, or in situ prostate cancer)
 - If the investigator, after consultation with the sponsor-designated medical monitor, determines that a systemic hypersensitivity reaction has occurred related to study drug administration, the participant should be permanently discontinued from the investigational drug
 - Onset of pregnancy in a female participant
 - Occurrence of any other treatment-emergent AE (TEAE), SAE, or clinically significant finding for which the investigator believes that permanent study drug discontinuation is the appropriate measure to be taken

- Inadvertent enrollment if continued treatment with study drug would not be medically appropriate.
- PHQ-9 score ≥ 15
 - Participants should be referred to a mental health professional (MHP) to assist in deciding whether the subject should be discontinued from study drug. If a participant's psychiatric disorder can be adequately treated with psycho- and/or pharmacotherapy, then the subject, at the discretion of the investigator (in agreement with the MHP), may be continued in the trial on randomized therapy.
- in addition, study drug may be discontinued if participants:
 - answered "yes" to Question 4 (Active Suicidal Ideation with Some Intent to Act, Without Specific Plan) on the "Suicidal Ideation" portion of the C-SSRS
 - or**
 - answered "yes" to Question 5 (Active Suicidal Ideation with Specific Plan and Intent) on the "Suicidal Ideation" portion of the C-SSRS
 - or**
 - answered "yes" to any of the suicide-related behaviors (Actual attempt, Interrupted attempt, Aborted attempt, Preparatory act or behavior) on the "Suicidal Behavior" portion of the C-SSRS

Note: A psychiatrist or appropriately trained professional may assist in the decision to discontinue the participant.

- **Discontinuation due to a hepatic event or liver test abnormality**

- Participants who are discontinued from IP due to a hepatic event or liver test abnormality should have additional hepatic safety data collected via eCRF
- Discontinuation of the IP for abnormal liver tests **should be** considered by the investigator when a participant meets 1 of the following conditions after consultation with the Lilly designated medical monitor:
 - ALT or aspartate aminotransferase (AST) $>8X$ ULN
 - ALT $>2X$ baseline value or ≥ 300 U/L, whichever occurs first, if baseline ALT $\geq 2X$ ULN
 - ALT or AST $>5X$ ULN for more than 2 weeks
 - ALT or AST $>3X$ ULN and TBL $>2X$ ULN or international normalized ratio (INR) >1.5

- ALT or AST >3X ULN with the appearance of fatigue, nausea, vomiting, right-upper-quadrant pain or tenderness, fever, rash, and/or eosinophilia (>5%)
- ALP >3X ULN
- ALP >2.5X ULN and TBL >2X ULN
- ALP >2.5X ULN with the appearance of fatigue, nausea, vomiting, right-upper-quadrant pain or tenderness, fever, rash, and/or eosinophilia (>5%)

Participants who stop the study drug permanently should continue to attend all scheduled study visits to collect all planned efficacy and safety measurements. Participants who stop the study treatment post-randomization and prior to 72 weeks but are unwilling to attend remaining scheduled visits should return for Visit 99 for a final weight measurement. If these participants are unwilling to attend Visit 99, their refusal to attend should be documented in the patient medical record.

See the SoA for data to be collected at the time of intervention discontinuation and follow-up and for any further evaluations that need to be completed.

7.1.1. Temporary Study Drug Discontinuation

In certain situations, after randomization, the investigator may need to temporarily interrupt study drug. Every effort should be made by the investigator to maintain participants on study drug and to restart study drug after any temporary interruption, as soon as it is safe to do so. Distribution of study medication at the correct dose will be per IWRS instructions.

If study drug interruption is...	then...
2 consecutive doses or less	participant restarts study drug at last administered dose, as per escalation schedule.
3 consecutive doses or more	participant restarts study drug (at 5 mg, managed by IWRS) and repeats dose escalation scheme.
due to an AE	the event is to be documented and followed according to the procedures in Section 8.3 of this protocol.
due to intolerable persistent GI AE	participants should be treated as suggested in Section 6.6.2.

Abbreviations: AE = adverse event; GI = gastrointestinal; IWRS = interactive web response service.

Investigators should inform the sponsor that study drug has been temporarily interrupted. The data related to temporary interruption of study treatment will be documented in source documents and entered on the eCRF.

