4.1. Overall Design

Study 18F-MC-GPHL is a Phase 3, multicenter, randomized, parallel, placebo-controlled, double-blinded, 72-week study that will investigate the safety and efficacy of treatment with tirzepatide 10 mg and 15 mg QW SC compared with placebo QW SC, in conjunction with a reduced-calorie diet and increased physical activity, on weight management in participants with T2DM who have obesity (body mass index [BMI] ≥ 30 kg/m²) or are overweight (BMI ≥ 27 kg/m²).

Study participants will be randomized in a 1:1:1 ratio (tirzepatide 10 mg QW, tirzepatide 15 mg QW, and placebo). An upper limit of 70% enrollment of women will be used to ensure a sufficiently large sample of men. In addition, an upper limit of 30% enrollment of participants treated with SU will be used to allow sufficient enrollment of participants treated with other antihyperglycemic medications (AHMs).

All participants will undergo a 3-week screening period, a 72-week treatment period (including a 20-week dose escalation and a 52-week dose maintenance period), and a 4-week safety follow-up period.

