Study drug dose escalation is double-blinded and will be managed via the interactive web-response system (IWRS). The starting dose is 2.5 mg QW (or matching placebo) for 4 weeks, then the dose is increased by 2.5 mg (or matching placebo) every 4 weeks (2.5 to 5 to 7.5 to 10 mg) for those randomized to 10 mg, continuing to 12.5 to 15 mg for those randomized to 15 mg. The dose is then maintained for the remainder of the study. In participants who experience intolerable GI symptoms, the dose can be changed as described in the Section 6.6.2.

At each of the 8 scheduled telephone visits, procedures will include:

- collection of AEs, PCs, and concomitant medications
- review of SMBG values and hypoglycemic events collected in the diary

- administration of Mental Health questionnaires
- review of participant diary information (to include reinforcement and compliance assessments for study drug administration and lifestyle goals)

Participants should be instructed to contact the investigative site for assistance as soon as possible if they experience any difficulties administering their study medication. Participants should also be advised about the appropriate course of action in the event that study drug is not taken at the required time (late/missing doses).

Study participants will be permitted to use concomitant medications that they require during the study, except certain excluded medications (see Section 5.2) that may interfere with the assessment of efficacy and safety characteristics of the study treatments.

Visit 99

Visit 99 is only applicable to participants who discontinue the study treatment prematurely (before Week 72) and decline to complete the remaining scheduled study visits. These participants will be asked to return for Visit 99 at 72 weeks \pm 7 days after randomization (See Section 7.2.1.). This visit is critical to ensure complete data collection for the primary weight loss endpoint.

Participants should attend this visit in the fasting state. Procedures to be completed are:

- measurement of weight and waist circumference
- listing of concomitant medications
- assessment of AEs, and
- completion of the Mental Health questionnaires (after the AE assessment).

For participants unwilling to attend this visit, their refusal to attend should be documented in the participant medical record.

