 - although there were no head-to-head clinical trials comparing tirzepatide with the current FDA-approved medications for chronic weight management, based on data from GPGB, it is unlikely that tirzepatide 5 mg will demonstrate significant benefit over existing treatment options and address the unmet need of achieving greater than 10% weight loss to provide greater metabolic and functional benefits to people with obesity

To address the decreased tolerability and increased treatment discontinuation in the 15-mg arm observed in GPGB, Lilly conducted the Phase 2 study GPGF to investigate the impact of different starting doses and escalation regimens on tolerability. Slower dose escalation and smaller dose increments are anticipated to improve tolerability. Dosing algorithms starting at a low dose of 2.5 mg accompanied by dose escalation of 2.5 mg increments every 4 weeks should permit time for development of tolerance to GI events and are predicted to minimize GI tolerability concerns. The maximum proposed dose of 15 mg maintains an exposure multiple of 1.6 to 2.4 to the no-observed adverse effect level doses in 6-month monkey and rat toxicology studies.

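### Protocol 7.1.1 is inconsistent for participants last dosed at 2.5 mg: a gap of three or more doses restarts them at a higher dose than a shorter gap does

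*Protocol*

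**What the plan says.** Protocol 7.1.1 (Temporary Study Drug Discontinuation) sets the restart by length of gap. For two or fewer consecutive missed doses, the "participant restarts study drug at last administered dose, as per escalation schedule". For three or more, the "participant restarts study drug (at 5 mg, managed by IWRS) and repeats dose escalation scheme". Neither row refers to how far the participant had titrated.

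Protocol 4.1.1.2.2 (Treatment Period) defines the scheme: "The starting dose is 2.5 mg QW (or matching placebo) for 4 weeks". From there it climbs in 2.5 mg steps at 4-week intervals, ending at 10 mg in the lower-dose arm and at 15 mg in the higher-dose arm. Protocol 4.1 gives the overall timing: "a 72-week treatment period (including a 20-week dose escalation and a 52-week dose maintenance period").

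Protocol 4.3 (Justification for Dose) gives the reason for the slow start. "Dosing algorithms starting at a low dose of 2.5 mg accompanied by dose escalation of 2.5 mg increments every 4 weeks" are expected to allow gastrointestinal (GI) tolerance to develop.

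Two cross-references bear on the GI route. Protocol 6.6.2 states: "Management of study drug after interruptions >1 dose is discussed in Section 7.1.1". The 7.1.1 row for persistent intolerable GI events states that "participants should be treated as suggested in Section 6.6.2". The SAP contains no restart rule.

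**The concern.** A restart rule graded by length of interruption would be expected to give the same or a lower dose after a longer gap. For one group the two rows do the opposite. Someone whose last dose was 2.5 mg goes back to 2.5 mg after two missed doses but on to 5 mg after three. The longer-gap row also tells that participant to repeat a scheme whose defined first step is 2.5 mg, without saying whether that step is included.

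What is at stake is tolerability and clarity for sites. The protocol describes the GI events as dose dependent and presents the 2.5 mg start as its safeguard. Read literally, the longer-gap row can take a participant past most of that step straight after a period off drug.

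**Working it through.** **Inputs.** Start 2.5 mg, step 2.5 mg, interval 4 weeks (Protocol 4.1.1.2.2). Escalation length 20 weeks (Protocol 4.1). Restart rows from Protocol 7.1.1.

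**1. Reproduce the stated escalation length.** Weeks to target = (target − start) / step × interval. For 15 mg this is (15 − 2.5) / 2.5 × 4 = 20 weeks, as stated. For 10 mg it is (10 − 2.5) / 2.5 × 4 = 12 weeks. The scheme has been read correctly.

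**2. Apply both restart rows to every possible last dose.**

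| Last dose (mg) | Restart, gap ≤2 doses | Restart, gap ≥3 doses | Difference |
|---|---|---|---|
| 2.5 | 2.5 | 5 | +2.5 |
| 5 | 5 | 5 | 0 |
| 7.5 | 7.5 | 5 | −2.5 |
| 10 | 10 | 5 | −5 |
| 12.5 | 12.5 | 5 | −7.5 |
| 15 | 15 | 5 | −10 |

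The order reverses in the first line only.

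**3. Compare the repeat with the defined scheme.** From 5 mg, reaching 10 mg takes (10 − 5) / 2.5 × 4 = 8 weeks and reaching 15 mg takes (15 − 5) / 2.5 × 4 = 16 weeks. The defined scheme takes 12 and 20. The difference is one 4-week step, the 2.5 mg step. For a participant who has already reached 5 mg or more, the explicit 5 mg in the row simply sets where the repeat begins. For one still at 2.5 mg, it leaves open whether the unfinished step is meant to be dropped.

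**4. Check against the calendar.** The 2.5 mg doses fall at Weeks 0, 1, 2 and 3. Restart week = week of last dose + doses missed + 1. The calendar dose is 5 mg in Weeks 4 to 7.

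| 2.5 mg doses taken | Restart week after 3 misses | Calendar dose (mg) | Row gives (mg) | 2.5 mg doses bypassed |
|---|---|---|---|---|
| 1 | 4 | 5 | 5 | 3 of 4 |
| 2 | 5 | 5 | 5 | 2 of 4 |
| 3 | 6 | 5 | 5 | 1 of 4 |
| 4 | 7 | 5 | 5 | 0 of 4 |

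So 5 mg does not exceed the calendar step. But the shorter-gap row does not follow the calendar. After four doses and two misses, restart falls at Week 3 + 2 + 1 = 6, where the calendar dose is 5 mg and the row gives the last dose, 2.5 mg.

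**5. Look for an exception elsewhere.** Protocol 6.6.1 bars dose changes except for intolerable GI symptoms. Protocol 6.6.2 sends gaps of more than one dose to 7.1.1, and the persistent-GI row of 7.1.1 sends the reader back to 6.6.2. None of these addresses a last dose of 2.5 mg.

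**The case against.** The best defence is the calendar. A participant who misses three doses after starting at Week 0 resumes at Week 4 or later, when 5 mg is due anyway, so no one is taken above schedule. That stands as a limit on the harm. It does not remove the inconsistency, because the shorter-gap row is tied to the dose last given. Its added reference to the escalation schedule makes the row ambiguous rather than calendar-based.

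A second defence is that the parenthesis in the longer-gap row deliberately fixes the restart point, and a restart rule need not equal the first-ever dose. That also stands for anyone who has reached 5 mg or more. A reader might infer from the mismatch with 4.1.1.2.2 that the rule is wrong for all participants; the table in step 2 does not support that.

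Third, dispensing is managed by IWRS, and the Appendix 9 flowchart on GI management is not reproduced in the text available. Either might handle the 2.5 mg case. A reader might equally infer that IWRS would dispense 5 mg to these participants. The documents contain no IWRS specification, so neither can be asserted.

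Finally, a reader might infer a knock-on effect on early discontinuation and missing data. The documents do not support a claim of that kind. Participants who stop study drug are asked to keep attending visits or to return for Visit 99 (Protocol 7.1), and the treatment-regimen estimand uses data regardless of adherence (SAP 1.1.2.1). Only the efficacy estimand drops data after discontinuation, and nothing allows the effect to be sized.

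**Conclusion.** Wrong as written, minor severity. For participants last dosed at 2.5 mg, the two gap-length rows of Protocol 7.1.1 give a higher restart dose after the longer gap (5 mg against 2.5 mg). The instruction to repeat the scheme is also undefined for them, since that scheme starts at 2.5 mg for 4 weeks.

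The reach is narrow: a gap of at least three doses beginning after one of doses 1 to 4. The drug dose changes only in the tirzepatide arms, because placebo participants restart on matching placebo. Interruptions for persistent GI events have their own row, although it leads back to the same table for gaps of more than one dose. The documents give no early interruption rate, so the number affected is unknown; it is probably small.

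The conclusion rests on the plain wording of the rows and on there being no exception in material that cannot be seen here (the IWRS configuration and the Appendix 9 figure). No power, alpha or sample size figure depends on this point.

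**What to change.** Reconcile the two gap-length rows of Protocol 7.1.1 with each other and with Protocol 4.1.1.2.2 for participants whose last dose was 2.5 mg. State what repeating the escalation scheme means for them, including where it begins. Confirm that the IWRS configuration and the Appendix 9 flowchart match the reconciled text. Which dose applies is a clinical decision for the sponsor, and none is proposed here.

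The cost is a wording change in one table and one system check. The SAP needs no change.

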7.2. Participant Discontinuation/Withdrawal from the Study

To minimize the amount of missing data and to enable assessment of study objectives as planned in the study protocol, every attempt will be made to keep participants in the study irrespective of the following:

- adherence to or discontinuation from study drug
- adherence to visit schedule
- missing assessments
- study drug discontinuation due to AE
- development of comorbidities
- development of clinical outcomes

The circumstances listed above are *not* valid reasons for discontinuation from the study.

A participant may withdraw from the study:

- at any time at his/her own request
- at the request of his/her designee (for example, parents or legal guardian)
- at the discretion of the investigator for safety, behavioral, compliance, or administrative reasons
- if enrolled in any other clinical study involving an IP or enrolled in any other type of medical research judged not to be scientifically or medically compatible with this study
- if the participant, for any reason, requires treatment (pharmacological, device based or surgical) that has been demonstrated to be effective for treatment of the study indication, discontinuation from the study occurs prior to introduction of the new treatment

Female participants will be withdrawn from the study if the participant becomes pregnant.

[figure not shown]
Participation in the study can be stopped for medical, safety, regulatory, or other reasons consistent with applicable laws, regulations, and good clinical practice (GCP). Participants who agree to provide information relevant to any trial endpoint at the end of the study are not considered to have discontinued from the study.

At the time of discontinuing from the study, if possible, an ED visit should be conducted, as shown in the SoA (Section 1.3) (see also Section 4.1.1). See SoA for data to be collected at the time of study discontinuation and safety follow-up and for any further evaluations that need to be

completed. The participant will be permanently discontinued both from the study intervention and from the study at that time.

If the participant withdraws consent for disclosure of future information, the sponsor may retain and continue to use any data collected before such a withdrawal of consent. If a participant withdraws from the study, he/she may request destruction of any samples taken and not tested, and the investigator must document this in the site study records.

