6.4. Study Intervention Compliance

Participant compliance with study intervention will be assessed at each visit. Compliance will be assessed by direct questioning and counting of unused study drug and/or empty cartons returned. Study drug compliance will be determined by the following:

- Study drug administration data will be recorded by the participant and reviewed by the investigator at each study visit.
- The participants will be instructed to return any unused study drug and/or empty cartons at the next visit to the study site for the purpose of performing drug accountability.

Treatment compliance for each visit interval is defined as taking at least 75% of the required doses of study drug. Similarly, a participant will be considered significantly noncompliant if he or she is judged by the investigator to have intentionally or repeatedly taken more than the prescribed amount of medication (more than 125%).

In addition to the assessment of a participant's compliance with the study drug administration, other aspects of compliance with the study treatments will be assessed at each visit based on the participant's adherence to the visit schedule, completion of study diaries, and any other parameters the investigator considers necessary.

Participants considered to be poorly compliant with their medication and/or the study procedures will receive additional training and instruction, as required, and will be reminded of the importance of complying with the protocol.

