10.12. Appendix 12: Abbreviations

Term	Definition
ADA	antidrug antibody
AE	adverse event: Any untoward medical occurrence in a patient or clinical investigation subject administered a pharmaceutical product that does not necessarily have a causal relationship with this treatment. An adverse event can therefore be any unfavorable and unintended sign (including an abnormal laboratory finding), symptom, or disease temporally associated with the use of a medicinal (investigational) product, whether or not related to the medicinal (investigational) product.
AESI	adverse event of special interest
AHM	antihyperglycemic medications
ALP	alkaline phosphatase
ALT	alanine aminotransferase
ANCOVA	analysis of covariance
AST	aspartate aminotransferase
BG	blood glucose
BMI	body mass index
BMR	basal metabolic rate
CEC	clinical endpoint committee
CFR	Code of Federal Regulations
CHF	congestive heart failure
CIOMS	Council for International Organizations of Medical Sciences
CK	creatine kinase
CKD-EPI	Chronic Kidney Disease-Epidemiology
CONSORT	Consolidated Standards of Reporting Trials
complaint	A complaint is any written, electronic, or oral communication that alleges deficiencies related to the identity, quality, purity, durability, reliability, safety or effectiveness, or performance of a drug or drug delivery system.
compliance	Adherence to all study-related, GCP, and applicable regulatory requirements.
CONSORT	Consolidated Standards of Reporting Trials

CRF	case report form
CRP	clinical research physician: Individual responsible for the medical conduct of the study. Responsibilities of the CRP may be performed by a physician, clinical research scientist, global safety physician or other medical officer.
CSR	clinical study report
C-SSRS	Columbia-Suicide Severity Rating Scale
CT	computed tomography
CTA	Clinical Trial Agreement
DNA	deoxyribonucleic acid
DPP-4	dipeptidyl-peptidase-4
EAS	efficacy analysis set
ECG	electrocardiogram
eCRF	electronic case report form
ED	early discontinuation
EDC	electronic data capture
eGFR	estimated glomerular filtration rate
EMA	European Medicines Agency
enroll	The act of assigning a participant to a treatment. Participants who are enrolled in the study are those who have been assigned to a treatment.
enter	Participants entered into a study are those who sign the informed consent form directly or through their legally acceptable representatives.
ERB	ethical review board
FAS	full analysis set
FDA	Food and Drug Administration

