1.1.2. Estimands

1.1.2.1. Estimands for Co-primary Endpoints

The primary clinical question of interest is: What is the intervention difference between QW tirzepatide 10 mg and/or 15 mg and placebo in mean percent change in body weight and proportion of participants who achieve $\geq 5\%$ body weight reduction from randomization to 72 weeks in participants with T2DM, who have obesity (BMI ≥ 30 kg/m²) or overweight (BMI ≥ 27 kg/m²)?

For primary disclosure of Study GPHL including submission to the US Food and Drug Administration (FDA)

The estimand is described by the following attributes:

- Population: all randomized participants who received at least 1 dose of study drug.
- Co-primary endpoints: mean percent change, from randomization to Week 72, in body weight, AND percentage of study participants who achieve $\geq 5\%$ body weight reduction from randomization to Week 72.
- Treatment condition of interest: tirzepatide 10 mg and/or 15 mg versus placebo, regardless of study drug adherence.
- Handling of intercurrent events: the intercurrent event leading to treatment discontinuation for any reason is addressed by the treatment condition of interest attribute and handled by treatment policy strategy as described in ICH E9 (R1) Addendum (ICH 2019). Further details can be found in Section 4.3.2.1.

- Population-level summary: difference in mean changes between treatment conditions, AND difference in response percentage between treatment conditions as assessed by odds ratio.

Rationale for estimand: It aims to reflect treatment effect among participants with T2DM and with obesity or overweight, irrespective to the compliance to the planned course of treatment.

This *de facto estimand* is referred to as the “treatment regimen” estimand in the latter sections of this document, which is equivalent to the “hybrid” estimand as stated in the protocol.

For other purposes

The estimand is described by the following attributes:

- Population: all randomized participants who received at least 1 dose of study drug.
- Co-primary endpoints: mean percent change from randomization to Week 72 in body weight, AND percentage of study participants who achieve $\geq 5\%$ body weight reduction from randomization to Week 72.
- Treatment condition of interest: tirzepatide 10 mg and/or 15 mg versus placebo, excluding data after discontinuation of study drug.

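### Protocol 7.2 says poor adherence is no reason to leave the study, then lets investigators withdraw participants for compliance; the two lists need reconciling

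*Protocol*

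**What the plan says.** Protocol Section 7.2 opens with a retention rule meant to limit missing data. Participants are to be kept in the study whatever happens on a list that includes "adherence to or discontinuation from study drug", "adherence to visit schedule" and missing assessments. It closes that list firmly: "The circumstances listed above are *not* valid reasons for discontinuation from the study".

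The next list in the same section gives the grounds on which a participant may be withdrawn. One of them is "at the discretion of the investigator for safety, behavioral, compliance, or administrative reasons". No text there narrows the word *compliance*. Section 7.2 adds that someone discontinued from the study leaves both study drug and study at that point, with an early discontinuation visit if possible. It also says that people who agree to give endpoint information at the end of the study do not count as discontinued.

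SAP Section 1.1.2.1 defines the estimand for US submission and primary disclosure as "Treatment condition of interest: tirzepatide 10 mg and/or 15 mg versus placebo, regardless of study drug adherence", with a treatment-policy strategy for stopping treatment.

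**The concern.** A treatment-policy estimand needs the Week 72 weight of people who took the drug badly as much as of those who took it well. If investigators may end follow-up because of poor compliance, the missing data depend on post-randomization behaviour that is plausibly related to weight. The gap is also avoidable, because the participant may have been willing to be weighed.

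There is a second effect. SAP Section 4.3.2.3 imputes most missing Week 72 data from retrieved dropouts, that is, people in the same arm measured after stopping drug. If someone has already stopped drug and would have stayed in follow-up, withdrawing them adds one missing value and removes one potential donor. With too few donors the SAP falls back on placebo-based imputation, which then also applies to data missing because of exceptional circumstances.

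**Working it through.** **Step 1. Does compliance mean the same thing as the excluded events?** Setting the passages side by side:

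| Not a valid reason (Protocol 7.2, first list) | Covered by compliance elsewhere in the protocol? |
|---|---|
| Poor adherence to study drug | Yes. Section 6.4: "Treatment compliance for each visit interval is defined as taking at least 75% of the required doses of study drug" |
| Poor adherence to visits | Yes. Section 6.4 counts keeping to the visit schedule among the aspects of compliance assessed at each visit |
| Missing assessments | Yes, through the glossary in Section 10.12: "Adherence to all study-related, GCP, and applicable regulatory requirements" |

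The word therefore includes the excluded events. It is also wider than them: it covers GCP and regulatory requirements, and Section 6.4 mentions intentional or repeated use above 125% of the prescribed amount.

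**Step 2. Is withdrawal the protocol's usual response?** No. Section 6.4 answers poor compliance with retraining and reminders. Sections 6.6.2 and 7.1 keep people who stop study drug in follow-up. The compliance ground in Section 7.2 is out of line with both.

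**Step 3. Would the Week 72 weight be recovered anyway?** Not clearly.
- Protocol Section 4.1.1.2.2 and the notes to Section 1.3 describe Visit 99 for people who stop treatment early and decline the remaining visits, or who want to leave. Neither describes someone the investigator removed.
- SAP Section 1.2 is wider and applies Visit 99 to people who stop treatment before Week 72. Sites, however, work from the protocol.
- The sentence in Section 7.2 about agreeing to give information depends on someone asking.
- Visit 99 measures weight and waist circumference. It does not include HbA1c, fasting glucose, lipids or blood pressure, so those key secondary endpoints stay missing even if it takes place.

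**Step 4. Is power affected?** Inputs from Protocol Section 9.2: 300 per arm, 25% dropout, difference 11 points, SD 10, responder rates 25% and 90%, two-sided alpha 0.025 per dose.
- Evaluable per arm: 300 × (1 − 0.25) = 225.
- Means: 11 / (10 × √(2/225)) = 11 / 0.943 = 11.67, against a critical value of about 2.25.
- Proportions: (0.90 − 0.25) / √[(0.25 × 0.75 + 0.90 × 0.10)/225] = 0.65 / 0.0351 = 18.5, against about 2.24.
- Both give power above 99.9%, which agrees with the stated figure of more than 90%.
- At 50% loss (150 per arm) the ratios are 9.53 and 15.1, and power is still above 99.9%. Without dropout, 90% power needs 21 per arm for means and 12 for proportions.

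**Step 5. Can the bias be sized?** If a fraction w of an arm is withdrawn on this ground, and their imputed weight changes miss the true ones by δ points on average, the arm mean is off by w × δ. The documents give neither quantity. Even the sign of δ is open. Someone who was still taking some doses would be imputed from people who had stopped altogether, or from placebo, and that need not favour tirzepatide.

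**The case against.** The strongest reply is that the two lists can be read together. The first is a specific prohibition; the second is general and permissive. Compliance is wider than missed doses or visits, so the discretionary ground could be kept for matters such as deliberate overuse or breaches of GCP. Section 6.4 points to retraining, and Sections 6.6.2 and 7.1 point to continued follow-up. On this view the text is loose, and no site is clearly licensed to remove poor adherers. The SAP's wider wording of Visit 99 and the sentence on agreeing to give information may also cover these participants. The disposition diagram in Protocol 7.2.1, which I could not read, may show their pathway and should be checked.

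Much of this stands. It shows that a careful site could avoid the problem. It does not show that the protocol prevents it, because nothing limits the discretionary ground to the wider matters.

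A reader might infer a definite bias. With assumed figures of 2–5% withdrawn (18–45 of 900) and an 8-point worse outcome, the arm mean would be off by 0.02 × 8 = 0.16 to 0.05 × 8 = 0.40 points. The documents do not support this. Neither input appears in them, and the sum holds only if withdrawn people are imputed as though they had adhered. Protocol Section 9.4.3.1 and SAP Section 4.3.2.3 impute from same-arm retrieved dropouts or placebo. SAP Section 4.3.2.4 adds placebo-based and return-to-baseline sensitivity analyses.

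A reader might also want to strike the behavioral and safety grounds. Behaviour is not in the first list. Safety touches that list only where study drug is stopped for an adverse event, and the protocol does not equate the two as it does compliance and adherence.

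**Conclusion.** The contradiction within Protocol 7.2 holds on the text, supported by Sections 6.4 and 10.12. Its consequence is a route to avoidable, adherence-related missing Week 72 data, and to fewer retrieved-dropout donors, under an estimand meant to ignore adherence. The size and direction of any bias are unknown; they depend on how many people are withdrawn on this ground and how closely retrieved dropouts resemble them. The planned imputation and sensitivity analyses soften the effect but cannot replace weights that could have been observed. Power is unaffected, and nothing here threatens the trial's main conclusion. It is a minor point that is worth correcting because the correction is easy.

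**What to change.** Reconcile the two lists in Protocol 7.2 by removing compliance as a ground for leaving the study, as distinct from study drug. Leave the safety and behavioral grounds unchanged, and leave the rules on stopping study drug as they are.

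Extend the Visit 99 wording in Protocol Sections 1.3 and 4.1.1.2.2 so that any participant withdrawn by the investigator is asked to attend the Week 72 assessment unless consent has been withdrawn. This brings the protocol nearer to SAP Section 1.2. It recovers weight and waist circumference, and so both co-primary endpoints, but not the laboratory or blood pressure endpoints.

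The cost is a short protocol amendment with the usual approvals (Protocol Section 10.1.1) and a note to sites. No analysis method changes. If compliance is recorded as its own reason, the disposition tables in Protocol Section 9.4.2.1 will show how often the ground was used in each arm.
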